#### **6.2.2.5 Assessment of Causality**

The investigator's assessment of an AE's relationship to study drug is part of the documentation process but is not a factor in determining what is or is not reported in the study.

The investigator will assess causality (ie, whether there is a reasonable possibility that the study drug caused the event) for all AEs and SAEs. The relationship will be classified as follows:

- Not related: The adverse event is considered unrelated to the study drug.
  - Another cause of the event is most plausible, or

- Clinically plausible temporal sequence is inconsistent with the onset of the event and the study treatment administration
  - A causal relationship is considered biologically implausible
- Possibly related: Based on evidence suggesting a causal relationship between the study drug and the AE, there is a reasonable possibility that the drug caused the event. The event follows a reasonable temporal sequence from the time of drug administration or follows a known response pattern to the study drug, but could also have been produced by other factors.
- Probably related: A reasonable temporal sequence of the event with drug administration exists and, based upon the known pharmacological action of the drug, known or previously reported adverse reactions to the drug or class of drugs, or judgment based on the investigator's clinical experience, association of the event with the study drug seems likely.

#### **6.2.2.6 Adverse Event of Special Interest**

The following are AESIs for this study:

- Grade  $\geq 2$  increased bilirubin
- Grade  $\geq 2$  increased ALT
- Grade  $\geq 2$  increased AST

The sponsor Medical Monitor will be notified promptly of AESIs. AESIs will be reported using the same process as for AEs.

#### **6.2.2.7 Follow-up of Adverse Events**

All AEs must be reported in detail on the appropriate page of the eCRF and followed until they are resolved, stable, or judged by the investigator to be not clinically significant.

### **6.2.3 Clinical Laboratory Testing**

Clinical laboratory testing will occur at screening, check-in, predose within 2 hours on each dosing day (Days 1, 8, and 15) (for Part B only), 3 days from dosing (Day 4, 11, 18), and at EOS. Clinical laboratory tests will be performed by the PPD Central Laboratory. Blood and urine samples will be collected under fasting conditions and will be prepared using standard procedures. If any concerning trends are seen during study, investigator can order additional testing for safety on PRN basis.

Repeat clinical laboratory tests may be performed at the discretion of the investigator, if necessary, to evaluate inclusion and exclusion criteria or clinical laboratory abnormalities. The clinical laboratory that will perform the tests will provide the reference ranges for all clinical laboratory parameters. Abnormal clinical laboratory values will be flagged as either high or low (or normal or abnormal) based on the reference ranges for each laboratory parameter.

The following clinical laboratory assessments will be performed:

Hematology	Absolute neutrophil count and differential, hematocrit, hemoglobin, mean corpuscular hemoglobin, mean corpuscular hemoglobin concentration, leukocytes-absolute counts and percentages (basophils, eosinophils, lymphocytes, monocytes, neutrophils), mean corpuscular volume, platelet count, red blood cell count, and red cell distribution width
Serum Chemistry	Alanine aminotransferase, albumin, alkaline phosphatase, aspartate aminotransferase, bilirubin (total + indirect and direct fractions), blood urea nitrogen, calcium, carbon dioxide, chloride, creatinine, gamma-glutamyltransferase, globulin, glucose, lactate dehydrogenase, phosphorus, potassium, sodium, total protein, uric acid, and creatine kinase
Urinalysis	Appearance, bilirubin, color, glucose, ketones, leukocytes, reflex microscopy (performed if dipstick is positive for protein or the blood value is 1+ or greater; and includes bacteria, casts, crystals, epithelial cells, red blood cells, and white blood cells), nitrites, occult blood, pH, protein, specific gravity, turbidity, and urobilinogen
Serology	Hepatitis B surface antigen, hepatitis C virus antibody, and human immunodeficiency virus antibody types 1 and 2 (screening only)
Other analyses	All participants: Urine drug screen (alcohol, amphetamines, barbiturates, benzodiazepines, cannabinoids, cocaine metabolites, cotinine, methamphetamines, methylenedioxymethamphetamine, and opiates [including heroin, codeine, and oxycodone]) Female participants: Follicle-stimulating hormone, urine pregnancy test/ serum pregnancy test (human chorionic gonadotropin)

#### **6.2.4 Vital Sign Measurements**

Vital signs will be measured at screening and check-in; within 60 to 90 minutes prior to plixorafenib dosing in each period; on each study day; and at EOS after the participant has been in the seated position for at least 5 minutes.

Vital signs will include systolic and diastolic blood pressure, pulse rate, respiratory rate, and body temperature.

#### **6.2.5 Electrocardiograms**

Single 12-lead ECG recordings will be made at screening, each dosing day (Days 1, 8, and 15)-predose within 2 hours, and at EOS after the participant has been in the supine position for at least 5 minutes. A single repeat measurement is permitted at screening for eligibility determination.

ECG assessments will include comments on whether the tracings are normal or abnormal, rhythm, presence of arrhythmia or conduction defects, morphology, any evidence of myocardial infarction, or ST-segment, T-Wave, and U-Wave abnormalities. In addition, measurements of the

following intervals will be measured and reported: RR interval, PR interval, QRS width, QT interval, and QT interval corrected for heart rate using Fridericia's formula.

### **6.2.6 Physical Examinations**

Physical examinations will be performed at screening, check-in, at each dosing day (Days 1, 8, 15), and at EOS (Day 19).

A full physical examination will be performed at screening and check-in. A symptom-driven physical examination may be performed at other times, at the investigator's or designee's discretion.

A full physical examination will include, at minimum, assessment of skin, head, ears, eyes, nose, throat, neck, thyroid, lungs, heart, cardiovascular, abdomen, lymph nodes, and musculoskeletal system/extremities. A brief physical examination will include, at minimum, assessment of skin, lungs, cardiovascular system, and abdomen (liver and spleen). Interim physical examinations may be performed at the discretion of the investigator, if necessary, to evaluate AEs or clinical laboratory abnormalities.

## **7. STATISTICAL ANALYSIS PLANS**

### **7.1 SAMPLE SIZE CALCULATIONS**

The number of participants is based on clinical and practical considerations and not on a formal statistical power calculation. The total sample size of 12 participants in Part A and 16 participants in Part B is considered sufficient for the objectives of the study.

### **7.2 ANALYSIS SETS**

The analysis populations are as follows:

- The PK population will include participants who receive at least 1 dose of plixorafenib with or without cobicistat and have sufficient concentration data to support accurate estimation of at least 1 PK parameter. Participants who experience vomiting within 2 times the median  $T_{\max}$  after study drug dosing will be excluded from the PK analysis.
- The safety population will include all participants who receive at least 1 dose plixorafenib with or without cobicistat.

### **7.3 STATISTICAL ANALYSIS**

Details of all statistical analyses will be described in a statistical analysis plan. All data collected will be presented in data listings. Data from participants excluded from an analysis population will be presented in the data listings, but not included in the calculation of summary statistics.

For categorical variables, frequencies and percentages will be presented. Continuous variables will be summarized using descriptive statistics (number of participants, mean, median, SD, minimum, and maximum).

Baseline demographic and background variables will be summarized overall for all participants. The number of participants who enroll in the study and the number and percentage of participants who complete the study will be presented. Frequency and percentage of participants who withdraw or discontinue from the study, and the reason for withdrawal or discontinuation, will also be summarized.

### **7.3.1 Pharmacokinetic Analyses**

Individual plasma concentration and time deviation data will be presented in a data listing. Plasma concentration data will be summarized by time point for each treatment (plixorafenib alone in fasted state, plixorafenib + cobicistat in fasted state or plixorafenib + cobicistat in fed state) using the following descriptive statistics: number of participants, arithmetic mean, SD, CV, geometric mean, geometric CV, median, minimum, and maximum. Individual and mean plasma concentration versus scheduled time profiles will be presented in figures on both linear and semilogarithmic scales.

The PK parameters of plixorafenib will be determined using noncompartmental methods based on the actual sampling times. All parameters will be calculated using Phoenix® WinNonlin® (Certara USA Inc., Princeton, New Jersey) Version 8.3 or higher. The individual PK parameters will be presented in data listings and summarized by treatment using the following descriptive statistics: number of participants, mean, SD, CV, median, minimum, and maximum. Geometric means will be included for  $AUC_{0-t}$ ,  $AUC_{0-inf}$ , and  $C_{max}$ .

If warranted, a linear mixed model with treatment as a fixed effect and participant as a random effect will be performed on the natural log-transformed values of  $AUC_{0-t}$ ,  $AUC_{0-inf}$ , and  $C_{max}$  to assess the effect of cobicistat and/or food on the PK of plixorafenib. The geometric least squares means and corresponding 90% CIs will be computed for  $AUC_{0-t}$ ,  $AUC_{0-inf}$ , and  $C_{max}$  of plixorafenib administered alone (Reference Treatment) versus plixorafenib with cobicistat and/or food (Test Treatments) by taking the antilog of the least squares means from the linear mixed-effect model on the natural logarithms of the corresponding PK parameters. A 90% CI for the ratio will be constructed as the antilog of the confidence limits of the mean difference.

It will be concluded that there is no relevant interaction of cobicistat or food on plixorafenib if the 90% CIs for  $AUC_{0-t}$ ,  $AUC_{0-inf}$ , and  $C_{max}$  ratios of the Reference Treatment to the Test Treatments are completely contained within the (80%, 125%) interval.

The statistical analysis plan will include a more detailed description of these analyses.

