### **4.4.3 Replacements**

Any participant who is withdrawn or discontinued from the study may be replaced.

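### The only PK crossover model in the documents has no period term, so a period effect can widen the 90% CIs and, once sequence balance is lost, can bias the ratios

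*Protocol*

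**What the plan says.** Protocol 7.3.1 and the matching synopsis paragraph give one inferential model for ln(AUC0-t), ln(AUC0-inf) and ln(Cmax): "a linear mixed model with treatment as a fixed effect and participant as a random effect". Its use is conditional ("If warranted, a linear mixed model with treatment as a fixed effect and participant as a random effect will be performed"), and no criterion for the condition is given. The model supplies the 90% CIs, and no relevant interaction is concluded if these "are completely contained within the (80%, 125%) interval".

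Protocol 3.1 and 3.2 and SAP Tables 3-2 and 3-4 list the sequences: six for Part A (three treatments, three periods) and four for Part B (four treatments, three periods). The SAP allocates equally to sequences.

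Three rules bear on balance. Section 4.4.3 says "Any participant who is withdrawn or discontinued from the study may be replaced", without saying which sequence the replacement takes. Section 7.2 removes participants who vomit early from the PK analysis. Section 7.4 rules out filling in missing data.

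Protocol 7.3.1 promises more detail in the SAP. SAP Sections 1 and 4 exclude PK methods and refer to a separate sponsor document, which was not supplied. No period term for PK appears in either document.

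**The concern.** The sequences place every treatment equally often in every period, but the stated model does not use that structure. If exposure drifts over the three dosing occasions, two things can follow.

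With complete data, the variation between periods is counted as residual error and the intervals are wider than they need be. With unbalanced data, treatment and period are no longer orthogonal, and part of the drift enters the treatment ratios.

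Both affect the intervals used for the 80-125% rule, in a study with 12 planned profiles per treatment in each part. The undefined condition adds a smaller problem: the plan does not fix whether the only inferential PK analysis it describes will be run.

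**Working it through.** The plan gives no power, interval width or variance to reproduce; the sample size rests "not on a formal statistical power calculation".

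**Inputs from the documents.** N = 12 (Part A) and 16 (Part B); the listed sequences with equal allocation (2 and 4 participants per sequence); 90% CI; limits 80% and 125%.

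**Assumptions.** Within-participant CV 30%, so s² = ln(1 + 0.30²) = 0.0862. Between-participant CV 50%, so the between variance is ln(1.25) = 0.2231. Linear drift on the log scale with total d from Period 1 to Period 3, so the period effects are -d/2, 0, +d/2 and their sum of squares is d²/2.

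**1. Balance.** In Part B the four sequences give A, B, D, C in Period 1; C, D, B, A in Period 2; and D, A, C, B in Period 3. Each treatment therefore occurs four times in each period, and the same count holds in Part A. Generalised least squares on the complete design gives a drift bias of exactly 0 in both parts, with or without period.

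**2. Degrees of freedom.** Part A: 36 - 1 - 11 - 2 = 22 without period, 20 with it; t(0.95) = 1.717 and 1.725. Part B: 48 - 1 - 15 - 3 = 29 and 27; t = 1.699 and 1.703.

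**3. Interval width.** Without period, E[MSE] = s² + N(d²/2)/df. The width relative to the model with period is (t without / t with) × √(E[MSE]/s²). Part A at d = 0.2: E[MSE] = 0.0862 + 12 × 0.02/22 = 0.0971, and (1.717/1.725) × √(0.0971/0.0862) = 1.057.

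| Total drift d | E[MSE] A | Width A | E[MSE] B | Width B |
|---|---|---|---|---|
| 0 | 0.0862 | -0.4% | 0.0862 | -0.2% |
| 0.1 | 0.0889 | +1.1% | 0.0889 | +1.3% |
| 0.2 | 0.0971 | +5.7% | 0.0972 | +5.9% |
| 0.3 | 0.1107 | +12.9% | 0.1110 | +13.2% |
| 0.4 | 0.1298 | +22.2% | 0.1303 | +22.7% |

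Setting the ratio to 1 gives the break-even drift: d = 0.053 in Part A (about 2.7% per period) and 0.039 in Part B (about 2.0%). Over CVs of 20% to 50% it is 1.8-4.3% per period (A) and 1.3-3.2% (B).

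**4. Bias after loss of balance.** Generalised least squares with d = 0.2 and a within-participant correlation of 0.2231/(0.2231 + 0.0862) = 0.72. Two Part B participants of one sequence leave after Period 1 and are not replaced.
- High-fat versus fasted: largest when B:D:A loses two. Two late fasted profiles are lost, and the ratio is multiplied by about 1.04.
- Low-fat versus fasted: factors from 0.978 to 1.023, depending on the sequence.
- One withdrawal instead of two: at most 1.8% (high-fat) and 1.0% (low-fat).

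Other cases, at 10% drift per period and correlations of 0.3-0.8:
- One participant wholly excluded: 1.8% (A), 1.9-2.0% (B).
- Replacement on a different sequence: 3.2% (A), 2.7-2.8% (B).
- Same-sequence replacement with the withdrawn participant's data removed: 0.

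With period in the model the bias is 0 in every case.

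**5. What this can do to the decision.** Using within-participant information only, the Part B variance factor for a treatment difference is 0.1875. With period, the half-width is 1.703 × √(0.1875 × 0.0862) = 0.2165, so an observed ratio of 1 has limits of 80.5% and 124.2%. Without period, at d = 0.2, it is 1.699 × √(0.1875 × 0.0972) = 0.2294, with limits of 79.5% and 125.8%. Under these assumptions the omission alone moves the interval across both limits.

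**The case against.** The strongest reply is that the final model may be in the PK analysis plan, which has not been seen. That stands. A reader might infer that the final analysis will omit period; the documents support only that the protocol model omits it and the SAP is silent.

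The drift sizes are assumptions, and the setting argues for small ones: confined healthy volunteers, standardised meals and 7-day dosing intervals. That also stands. At 5% drift per period the widening is only 0.1-3.0% over CVs of 20-50%, and below break-even the omission helps slightly. It would be wrong to say that leaving out period always widens the intervals.

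Nor does every withdrawal with replacement bias a ratio. A same-sequence replacement that takes the withdrawn participant's place restores balance. The protocol neither requires nor excludes this.

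With complete data, wider intervals make it harder to conclude no interaction, so the error is conservative for that rule. This is correct, but the bias after lost balance can go in either direction.

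Finally, the conditional opening might be read as a decision to be made after seeing the data. The text does not say so; it only leaves the condition undefined.

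**Conclusion.** The point holds as a conditional weakness of the stated model, and the correction is cheap. At CV 30%, omitting period widens the 90% CIs by about 1%, 6% and 22% at total drifts of 0.1, 0.2 and 0.4 log units, and narrows them by 0.2-0.4% at zero drift. The ratios are unbiased with complete, balanced data. In the Part B case examined, two participants lost from one sequence after Period 1 with drift 0.2, the bias reaches about 4%; with one lost it is under 2%. The CVs, the correlation and the drift are all assumed, because the documents give none.

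A reader might infer that the Part A result is in doubt. It is not: Protocol 1.2 reports increases of about two-fold in Cmax and three-fold in AUC with food, and biases of this size cannot overturn them. What is exposed is a Part B comparison lying close to 80% or 125%.

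**What to change.** In Protocol 7.3.1, the synopsis and the PK analysis plan, delete *If warranted* and state the model in full: ln(AUC0-t), ln(AUC0-inf) and ln(Cmax), with treatment and period as fixed effects and participant as a random effect, fitted within each part for the contrasts that part can estimate. If the PK plan already includes period, bring the protocol wording into line with it.

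This model cannot deliver one Part B primary objective, low-fat versus fasted with cobicistat. Part B has no fasted treatment with cobicistat; that treatment is in Part A only. The contrast needs a cross-part comparison and must be specified separately.

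It would also help to state which sequence a replacement takes and how the withdrawn participant's data are used, though this does not substitute for the period term.

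Cost: a line of model code and two residual degrees of freedom. With no period effect the CI is wider by 1.725/1.717, or 0.4%, in Part A and by 1.703/1.699, or 0.2%, in Part B. With complete balanced data the point estimates do not change.

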### **2.1 PRIMARY OBJECTIVE**

The primary objectives for Part A of the study are as follows:

- To examine the effect of food on the single dose PK of plixorafenib administered with cobicistat.
- To examine the effect of cobicistat administration on the single dose PK of plixorafenib.
- To determine the safety of plixorafenib administered alone and with cobicistat in a single dose regimen in healthy participants.

The primary objectives for Part B of the study are:

- To examine the effect of a high-fat and a low-fat meal versus fasted state on the single dose PK of plixorafenib administered alone.
- To examine the effect of a low-fat meal versus fasted state on the single dose PK of plixorafenib administered with cobicistat.
- To determine the safety of plixorafenib administered alone or with cobicistat (low-fat meal only) in a single dose regimen.

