**Table 3-1 Study Description for Part A**

Treatment Period	Screening	Check-in	Dosing	Confinement
1	Day -28 to -1	Day -1	Day 1	Day -1 to Day 19 (EOS)
2	N/A	N/A	Day 8	
3	N/A	N/A	Day 15	

N/A, not applicable; EOS, end of study

There will be a 7-day washout between dosing in each treatment period.

EOS visit will be conducted on Day 19.

A screening evaluation will be performed to determine each participant's eligibility for the study approximately 28 to 1 days before the first dose. Participants eligible for participation will report to the study facility 1 day before dosing in Treatment Period 1 for check-in.

On Day 1 of Treatment Period 1, eligible participants will be randomized to 1 of 6 treatment sequences: 1:2:3, 2:3:1, 3:2:1, 2:1:3, 3:1:2, 1:3:2. On the first day of each treatment period, each participant will receive one of the following treatments according to the sequence in which he or she is randomized:

- Treatment 1: 900 mg plixorafenib administered after overnight fast (fasted state).
- Treatment 2: 900 mg plixorafenib + 150 mg cobicistat administered after overnight fast (fasted state).
- Treatment 3: 900 mg plixorafenib + 150 mg cobicistat administered following a high fat, high caloric meal (fed state).

For Treatment 2 and Treatment 3, plixorafenib and cobicistat will be co-administered.

All participants will fast overnight (nothing to eat or drink except water) for at least 10 hours. Participants receiving Treatments 1 and 2 (fasted condition) will continue to fast for at least 4 hours after dosing.

Participants receiving Treatment 3 will receive a standard high fat ( $\geq 50\%$  of the total caloric content of the meal), high caloric meal (approximately 800 to 1000 calories) for breakfast before dosing and this meal should derive approximately 150, 250, and 500 to 600 calories from protein, carbohydrate, and fat, respectively (DHHS 2022). Participants must consume the entire meal within 30 minutes of serving; the percentage of meal consumed will be documented. Dosing must occur 30 minutes ( $\pm 5$  minutes) after the start of the meal. Participants receiving Treatment 3 will receive their next meal no less than 4 hours after dosing.

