**Table 3-2 Study Description for Part B**

Treatment Period	Screening	Check-in	Dosing	Confinement
1	Day -28 to -1	Day -1	Day 1	Day -1 to Day 19 (EOS)
2	N/A	N/A	Day 8	
3	N/A	N/A	Day 15	

N/A, not applicable; EOS, end of study.

There will be a 7-day washout between dosing in each treatment period. EOS visit will be conducted on Day 19.

A screening evaluation will be performed to determine each participant's eligibility for the study approximately 28 to 1 days before the first dose. Participants eligible for participation will report to the study facility 1 day before dosing in Treatment Period 1 for check-in.

On Day 1 of Treatment Period 1, eligible participants will be randomized to 1 of 4 treatment sequences: A:C:D, B:D:A, D:B:C, C:A:B. On the first day of each treatment period, each participant will receive one of the following treatments according to the sequence in which he or she is randomized:

- Treatment A: 900 mg plixorafenib administered after overnight fast (fasted state).
- Treatment B: 900 mg plixorafenib administered following a high-fat high caloric meal (fed state-high fat meal).
- Treatment C: 900 mg plixorafenib administered following a low-fat meal (fed state-low-fat meal).
- Treatment D: 900 mg plixorafenib administered with 150 mg cobicistat following a low-fat meal (fed state-low-fat meal).

All participants will fast overnight (nothing to eat or drink except water) for at least 10 hours.

- Participants receiving Treatment A (fasted condition) will continue to fast for at least 4 hours after dosing.
- Participants receiving Treatment B will receive a high fat ( $\geq 50\%$  of the total caloric content of the meal), high caloric meal (approximately 800 to 1000 calories) for breakfast before dosing and this meal should derive approximately 150, 250, and 500 to 600 calories from protein, carbohydrate, and fat, respectively.
- Participants receiving Treatments C and D will receive a low-fat meal (approximately 400 to 500 total calories, with 25% of the total caloric content of the meal from fat) for breakfast before dosing.

All participants receiving Treatments B, C, or D must consume the entire meal within 30 minutes of serving; the percentage of meal consumed will be documented. Dosing must occur 30 minutes ( $\pm 5$  minutes) after the start of the meal. Participants receiving Treatments B, C, and D will receive their next meal no less than 4 hours after dosing.

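### Protocol 7.3.1 makes plixorafenib alone the only reference, so no stated contrast isolates the food effect with cobicistat that primary objectives in Parts A and B ask for

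*Protocol*

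**What the plan says.** Protocol section 7.3.1, repeated in the synopsis, plans a mixed model on log AUC0-t, AUC0-inf and Cmax if warranted, with treatment fixed and participant random. The comparison is "plixorafenib administered alone (Reference Treatment) versus plixorafenib with cobicistat and/or food (Test Treatments". No relevant interaction of cobicistat or food is concluded if the 90% confidence intervals for the "ratios of the Reference Treatment to the Test Treatments are completely contained within the (80%, 125%) interval". Neither the protocol nor the SAP names any other reference or contrast.

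The food objectives with cobicistat in Protocol section 2.1 are:

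- Part A: "To examine the effect of food on the single dose PK of plixorafenib administered with cobicistat".
- Part B: "To examine the effect of a low-fat meal versus fasted state on the single dose PK of plixorafenib administered with cobicistat".

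The arms that bear on them (Protocol sections 3.1 and 3.2) are:

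- Part A Treatment 2: "900 mg plixorafenib + 150 mg cobicistat administered after overnight fast (fasted state".
- Part A Treatment 3: "900 mg plixorafenib + 150 mg cobicistat administered following a high fat, high caloric meal (fed state".
- Part B Treatment D, the only cobicistat arm in that part: "900 mg plixorafenib administered with 150 mg cobicistat following a low-fat meal (fed state-low-fat meal".

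Section 7.3.1 promises more detail in the SAP. SAP section 1 excludes PK analysis in favour of a separate PK analysis plan, and SAP section 4 likewise sends PK methods to a separate sponsor document.

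**The concern.** Part A's first primary objective holds cobicistat fixed and varies the meal. The written rule holds neither fixed: Treatment 3 differs from plixorafenib alone in both. A primary objective therefore has no stated estimate, and the conclusion about food rests on a ratio that contains the whole cobicistat effect.

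In Part B the comparisons of B and C with A are sound if the reference means Treatment A. The text does not say so, and A, B and C are all given without cobicistat. Treatment D against A again changes meal and cobicistat together, and Part B offers no fasted cobicistat arm to replace A. Its second primary objective is therefore not answered by any contrast within Part B.

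**Working it through.** The plan states no power or precision figure to reproduce. Protocol section 7.1 says that 12 and 16 participants are not based on a power calculation.

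**1. What each contrast estimates.** As ratios of geometric means, 3/1 = (2/1) × (3/2). The written contrast 3/1 equals the food effect with cobicistat only if cobicistat has no effect.

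**2. Size on the documents' figures.** Inputs:

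- 3/2: about 3-fold for AUC0-inf and 2-fold for Cmax (Protocol section 1.2, reading the fasted state there as fasted with cobicistat).
- 2/1: about 2- to 3-fold exposure in cancer patients, and 3.8-fold AUC and 2.7-fold Cmax at 900 mg in healthy participants on the previous formulation (Protocol section 1.1.1).

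| Measure | 3/2 | 2/1 | 3/1 = product |
|---|---|---|---|
| AUC | 3 | 2.0 | 6.0 |
| AUC | 3 | 3.0 | 9.0 |
| AUC | 3 | 3.8 | 11.4 |
| Cmax | 2 | 2.7 | 5.4 |

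The reported fold changes are in averages, so the products are approximate.

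**3. Can the written rule show no food effect?** Suppose 3/2 = 1. Then 3/1 equals the cobicistat effect, 2.0 to 3.8. With 12 participants and three periods, either contrast has variance 2s²/12 with 36 − 12 − 2 = 22 degrees of freedom, where s² = ln(1 + CV²). The documents give no within-participant CV, so a range is assumed. Simulation (400,000 draws) of the chance that the 90% interval lies within 80-125%:

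| Assumed CV | 3/2, true ratio 1 | 3/1, true ratio 2.0 or 3.8 |
|---|---|---|
| 15% | 0.94 | 0 |
| 20% | 0.70 | 0 |
| 30% | 0.16 | 0 |
| 40% | 0.01 | 0 |

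The chance for 3/1 was 0 at every CV tried, from 10% to 60%. Because the variance is the same, using 3/2 loses no precision.

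**4. Part B.** D/A = cobicistat effect × low-fat meal effect. D/C is the cobicistat effect after a low-fat meal. Neither is low-fat against fasted with cobicistat. An indirect estimate is (D/A in Part B) / (2/1 in Part A), since A and 1 are the same treatment.

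- Each pair of Part B treatments occurs together in 2 of the 4 sequences. With 4 participants per sequence, that is 8 participants.
- Within-participant variance of a Part B contrast: 2 × 3 / (8 × 4) × s² = 0.1875s², with 48 − 16 − 3 = 29 degrees of freedom.
- Variance of the indirect estimate: 0.1875s² + 0.1667s² = 0.354s², with 29 + 22 = 51 degrees of freedom if the within-participant variance is equal in both parts.

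The 90% interval runs from the estimate divided by a factor to the estimate multiplied by it:

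| Assumed CV | Part A direct contrast | Indirect cross-part contrast |
|---|---|---|
| 20% | 1.15 | 1.22 |
| 30% | 1.23 | 1.34 |
| 50% | 1.39 | 1.60 |

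**The case against.** The strongest reply is that the governing document has not been seen. The separate PK analysis plan may name 3/2, and the model, which is itself conditional, yields that contrast directly. This stands as a limit: the conflict is established for the protocol's wording, not for everything the sponsor has written.

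A second reply is that the right comparison seems to have been made. Protocol section 1.2 and SAP section 1 report plixorafenib plus cobicistat with the meal relative to the fasted state, and SAP section 10 says that analysis at the end of Part A informed Part B. A reader might infer from section 7.3.1 that the reported food effect is inflated by the cobicistat effect. The documents do not support that, since the reported figures read as 3 against 2.

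Nor would the Part A verdict change. A confidence interval contains its own estimate, so a ratio near 2 or 3 cannot have an interval inside 80-125%, and 3/1 would lie still further out. Opposing effects could in principle cancel in 3/1 and give a false finding of no interaction, but food would then have to lower boosted exposure, contrary to the Part A report.

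Three further points are weaker than they may look:

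- Writing the ratio as Reference to Test does not alter the decision, because 0.80 and 1.25 are reciprocals. A 3-fold increase would merely print as 0.33.
- The concentration summaries in section 7.3.1 list only "plixorafenib alone in fasted state, plixorafenib + cobicistat in fasted state or plixorafenib + cobicistat in fed state", which are the Part A arms. This is a presentation gap. SAP section 4 lists all seven treatments for its own outputs, although PK outputs may fall outside it.
- A reader might fault Part B for not requesting D against C. Part B has no primary objective on the cobicistat effect, so that omission misses no primary objective.

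**Conclusion.** The point holds for the protocol as written. Its single-reference rule gives no estimate for Part A's first primary objective. The contrast it does give for the fed cobicistat arm would be about 6- to 11-fold for AUC where the food effect is about 3-fold. The mixing of effects follows from the contrast and is present whatever the fold changes; the range itself is illustrative and rests on cobicistat effects from cancer patients and a previous formulation. With a cobicistat effect of 2- to 3.8-fold, the written rule could not show an absence of food effect with cobicistat.

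In Part A the defect lies in the named contrasts, not in the design, the model or the reported result. In Part B it goes further: with no fasted cobicistat arm, the second primary objective cannot be met by renaming the reference. Whether the PK analysis plan already deals with either matter cannot be determined from these documents.

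**What to change.** Replace the single-reference sentence in Protocol section 7.3.1 and the synopsis with named Test/Reference contrasts, and make the PK analysis plan agree:

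- **Part A:** 2/1 (cobicistat, fasted) and 3/2 (high-fat meal with cobicistat). Report 3/1 descriptively only.
- **Part B:** B/A and C/A, with the reference stated as Treatment A, fasted. D/A carries no food-effect conclusion. D/C may be reported as the cobicistat effect after a low-fat meal, but it does not answer the second primary objective.
- **Part B second primary objective:** either prespecify a cross-part comparison of D with Part A Treatment 2, for example (D/A)/(2/1), or reword the objective. The comparison should state its assumptions: the same fasted cobicistat effect in both groups of participants and, for the interval above, equal within-participant variance.
- **Decision rule:** apply 80-125% separately to each named contrast, with each conclusion limited to the factor that the contrast isolates.
- **Presentation:** write ratios as Test/Reference and list all seven treatments in the concentration summaries.

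For Part A and for B/A and C/A the cost is wording: same data, same model, different contrast statements. The cross-part comparison needs no new participants but is less precise and not randomised between parts. It should be specified as a planned analysis, because SAP section 4 allows pooling by treatment only as an optional exploratory step.
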